13.2 Independent Ethics Committee/Institutional review Board

The study and the patient informed consent form must be approved in writing by an appropriate IEC/IRB prior to enrollment of any study subjects.

Any changes to the protocol as well as a change of investigator, which is approved by the sponsor, must also be approved by the site's IEC/IRB and documentation of this approval provided to the sponsor/designee. Records of the IEC/IRB review and approval of all documents pertaining to this study must be kept on file by the investigator and are subject to inspection by Regulatory Authorities during or after completion of the study. SAEs must also be reported to the IEC/IRB (or as applicable).

Periodic status reports must be submitted to the IEC/IRB at least annually, as well as notification of completion or termination of the study. A copy of all reports submitted to the IEC/IRB must be sent to the sponsor/ designee.

The investigator shall ensure that an IEC/IRB shall be responsible for the initial and continuing review and approval of the proposed clinical study.

13.3 Subject Confidentiality

The Subjects Medical records and study data will be kept confidential in compliance with the applicable regulatory guidelines. However, as per the requirements regarding the monitoring of clinical studies and in fulfillment of his/her obligations to the sponsor, it is required that the investigator permit the study monitor, sponsor auditor, and/or regulatory authority representative to review that portion of the subject's medical record that is directly related to the study. This shall

include all study relevant documentation including subject medical histories to verify eligibility and other source documents.

As part of the required content of informed consent, the subjects must be informed that his/her medical chart may be reviewed by the sponsor, the sponsor's and/or regulatory authority's representatives. Should access to the medical record require a separate waiver or authorization, it is the investigator's responsibility to obtain such permission from the subject in writing before the subject is entered into the study.

14 DOCUMENTATION

14.1 Maintenance and Retention of Records

All records pertaining to the receipt and return of study supplies (particularly study medication) and copies of final case report form, worksheets and other pertinent source documents must be retained in accordance with the applicable requirements of the country where the study is being conducted as well as the country where the study will be submitted.

Essential documents must be retained until at least 2 years after the last approval of a marketing application in an ICH region and until there are no pending or contemplated marketing applications in an ICH region or until at least 2 years have elapsed since the formal discontinuation of clinical development of the investigational product. These documents will be retained for a longer period if required by the applicable regulatory requirements or by an agreement with the sponsor. It is the responsibility of the sponsor to inform the investigator/institution as to when these documents no longer need to be retained.

14.2 Case Report Forms (CRF)

Data will be documented in the eCRF to capture the trial related data from source document/any other pertinent documents.

SAE reporting by Investigator shall be done as per the regulatory requirements, and any related supporting information and/or documents shall be sent by appropriate mode of communication.

Subjects are not to be identified on eCRFs by name; appropriately coded identification and the subject's initials must be used. The investigator must keep a separate log of the subject's names and addresses.

14.3 Primary Source Documents

The investigator must maintain primary source documents supporting significant data for each subject's medical notes. These documents, which are considered "source data", should include (but not limited to) documentation of:

- Demographic information

- Evidence supporting the diagnosis/condition for which the subject is being studied
- General information supporting the subject's participation in the study
- General history and physical findings
- Hospitalization or Emergency Room records (if applicable)
- Each study visit by date, including any relevant findings/notes by the investigator(s), occurrence (or lack) of adverse events, and changes in medication usage, including the date the study drug commenced and completed.
- Any additional visits during the study
- Any relevant telephone conversations with the subject regarding the study or possible adverse events
- An original, signed informed consent for study participation
- The investigator must also retain all subject specific printouts/reports of tests/procedures performed as a requirement of the study.

14.4 Study Monitoring

The study will be monitored by the assigned monitor in compliance with Good Clinical Practices Guideline and applicable regulations. The investigator will be visited by a monitor prior to the study and at regular intervals during the course of the study. These visits are for the purposes of verifying adherence to the protocol, standard operating procedures (SOPs), GCP and applicable regulatory requirements.

The study monitor will review the informed consent forms and verify eCRF entries with the source documents (hospital/clinic records). The monitor will review the maintenance of regulatory documentation, drug accountability, and on a regular basis the progress of the study with the investigator and site personnel. At the end of the study, a closeout monitoring visit will be performed.

The coordinator and/or investigator should be available to answer questions or resolve data discrepancies/clarifications. Adequate time and space for these visits should be made available by the investigator and by the site personnel for the monitoring activities at site.

14.5 Audits and Inspections

During the course of the study and/or after it is going to be completed, one or more site visits may be undertaken by auditors as authorized representatives of the sponsor. The purpose of the audit is to determine whether or not the study is being conducted and monitored in compliance with recognized GCP guidelines and laws.

Additionally, the study may be inspected by regulatory agencies. These inspections may take place at any time during/after the study and are based on the local and international regulations.

14.6 Modifications to the Protocol

The procedures defined in the protocol will be carefully reviewed to ensure that all parties involved with the study fully understand the protocol. In order to ensure the validity of the data, no deviations from the protocol, with minimal exceptions, may be made unless the issue is broad enough to warrant revision of the protocol. Such revisions must be submitted to and have documented approval from the sponsor and the IEC/IRB prior to implementation.

All amendments to the protocol, which involve substantial changes in study design, procedure, analyses, will be submitted to regulatory authorities for prior approval.

16 FURTHER REQUIREMENTS AND GENERAL INFORMATION

16.1 Contract Research Organization for Clinical Operations

CRO will be responsible for administrative aspects of the study including, but not limited to, study initiation, monitoring, management of SAE reports, and data management. Before subjects are

screened at each study site, the study monitor will review study responsibilities with the investigators and other study site staff, as appropriate.

16.2 Clinical Data Management

Data Management will be performed by the sponsor's designated facility. Data entry screens will be designed to look like paper forms for data entry. User Acceptance Testing will be performed before making the study live for data entry. Once data entry is completed, activities like data validation, quality review, medical coding, database lock and datasets export etc. will be performed. All adverse events will be coded using the current version of MedDRA and concomitant medications will be coded using the current version of WHO DD (WHO Drug Dictionary). Further scope of Data Management activities will be explained in the study specific Data Management Plan and will be approved by the sponsor.

16.3 Ethics Committee Notification of Study Completion or Termination

The Regulatory Authority and the IRB/IEC in each country must be notified within 90 days of completion of the study or within 15 days if the study is terminated early or as per applicable regulatory requirements.

16.4 Insurance

The study will be covered with an appropriate insurance contract.

16.5 Study Report Signatory

Sponsor/CRO may designate one of the participating investigators as a signatory for the study report. This determination will be made by several factors, including but not limited to, the Investigator's experience and reputation in the studied indication, the Investigator's contribution to the study in terms of design, management, and/or subject enrollment, or by other factors determined to be relevant by sponsor.

## LIST OF ABBREVIATIONS

Abbreviation or special term	Explanation
AE	Adverse Event
ALT	Alanine transaminase
ANCOVA	Analysis of Covariance
AST	Aspartate transaminase
BMI	Body Mass Index
CI	Confidence Interval
eCRF	Electronic Case Report Form
CRO	Contract Research Organization
ECG	Electrocardiogram
FDA	Food and Drug Administration
LOCF	Last Observation Carried Forward
LS	Least Squares
MedDRA	Medical Dictionary for Regulatory Activities
mITT	Modified Intent to Treat
OA	Osteoarthritis
OTC	Over the Counter
POM	Pain On Movement
PP	Per Protocol
PSRM	Product Safety and Risk Management
RLD	Reference Listed Drug
SAE	Serious Adverse Event
SAP	Statistical Analysis Plan
SAS	Statistical Analysis System
SD	Standard Deviation
SE	Standard Error
SGOT	Serum Glutamic Oxaloacetic Transaminase
SGPT	Serum Glutamate-Pyruvate Transaminase
TEAE	Treatment-emergent Adverse Event
US	United States
VAS	Visual Analog Scale
WHO	World Health Organization
WOMAC	Western Ontario and McMaster Universities Osteoarthritis Index

## CHANGES FROM VERSION 1 TO VERSION 2

1. Additional subgroup descriptive summaries of WOMAC Pain Subscale score (for subjects with baseline WOMAC Pain Subscale score  $\leq 10$  and by Kellgren-Lawrence grade)
2. Additional summary of percentage of patients that used acetaminophen (paracetamol) at least once during the trial.
3. Average daily dose of acetaminophen is calculated only over days when acetaminophen was used.
4. Added forest plot for test/reference ration in various subgroups.

## 1. INTRODUCTION

The purpose of this statistical analysis plan (SAP) is to provide details of the statistical analyses that have been outlined within the protocol "A Randomized, Double blind, Three-arm, Parallel, Placebo-controlled, Clinical Study to Evaluate the Bioequivalence using Clinical Endpoint of Diclofenac Sodium Gel, 1% (Mylan Inc.) to Voltaren® Gel (Diclofenac Sodium Topical Gel) 1% (Novartis Consumer Health, Inc.) in Patients with Osteoarthritis (OA) of the Knee" version 1.1 dated May 3, 2017.

Mylan is developing a generic diclofenac sodium gel to the Reference Listed Drug (RLD) Voltaren® gel. This randomized, double-blind, three-arm, placebo-controlled, bioequivalence study with clinical endpoint has been designed to establish clinical equivalence and safety of Mylan's diclofenac gel in the symptomatic treatment of osteoarthritis of knee compared to Voltaren® gel and to establish superiority in efficacy of both compared to a placebo (vehicle) gel.

This SAP describes the study endpoints, derived variables, anticipated data transformations and manipulations, and other details of the analyses not provided in the study protocol. The SAP also outlines the statistical programming specifications for the tables, listings and figures.

## 2. OBJECTIVES

The primary objectives of this study are:

1. To determine the clinical equivalence of the Test Drug (Diclofenac sodium gel of 1% of Mylan Inc.) with the Reference Listed Drug (RLD) (Voltaren® Gel 1% of Novartis Consumer Health, Inc.) as measured by mean change from baseline in the Western Ontario and McMaster Universities Osteoarthritis Index (WOMAC) Likert (version 3.1) pain score.
2. To establish superiority of the Test Drug and Reference Listed Drug (RLD) over placebo in mean change from baseline in the WOMAC Likert (version 3.1) pain score.

The secondary objectives of this study are:

1. To assess the safety and tolerability of study treatments.
2. To determine the clinical equivalence of the Test Drug (Diclofenac Sodium gel) with the Reference Listed Drug (RLD) (Voltaren® Gel) as measured by mean change from

baseline in subjects whose baseline WOMAC Likert (version 3.1) pain scores are less than or equal to 10.

### **3. STUDY OVERVIEW**

#### **3.1 Study Design**

This is a double-blind, multiple-site, randomized, parallel-design study to investigate the bioequivalence with clinical endpoint of Mylan's Diclofenac Sodium Topical Gel, 1% to Voltaren® Gel, 1% (Novartis US) and to investigate that both the active products are superior to placebo.

Subjects will have to visit the clinic for the following visits during the study:

- Visit 1 – Screening visit (within 28 days prior to randomization)
- Visit 2 – Start of Placebo Run-in period (Day -11 to Day -7)
- Visit 3 – Randomization (baseline) visit (Day 0)
- Visit 4 – Interim visit (Week 2/Day 14 ± 4)
- Visit 5 – End of study (Week 4/Day 28 ± 4)/Early termination visit

After informed consent process and completion of all screening assessments, the eligible subjects will be requested to stop the currently ongoing osteoarthritis drug therapy. The wash out period (run-in period) of 7 days or  $\geq$  5 half-life of previous osteoarthritis drug therapy, whichever is longer, will be maintained before the baseline visit. Subjects will undergo at least 7 days of placebo run-in period. In case subject extends run-in period beyond 11 days, continuation of the subject will be decided in consultation with Medical monitor.

The Pain on Movement (POM) score on a Visual Analog Scale (VAS) and Western Ontario and McMaster Universities Osteoarthritis Index (WOMAC Likert version 3.1) pain score will be recorded at the start of run-in Period and at the end of run-in Period (i.e. immediately prior to randomization on the day of baseline visit). Recording of the VAS will be done for both knees and recording of the WOMAC pain score will be done for the target knee. Target knee is defined as the knee that is more painful and will be identified during the screening visit.

During the washout period, subjects will undergo a single-blind placebo run-in period where the subjects will not be aware of the placebo nature of the drug. Subjects will be provided with

placebo gel for the administration. Approximately 4 g dose of placebo gel will be applied to the target knee four times daily for at least 7 days. First administration of gel will be done at the study center.

At the baseline visit, subjects will be randomly assigned in 1:1:1 ratio to Mylan's Diclofenac Sodium Topical Gel 1%, Voltaren® Gel 1% (Reference Listed Drug) and Placebo. All the subjects will be instructed to apply the gel next day (Day 1) onwards. All subjects will be applying approximately 4 g dose of either Mylan's Diclofenac Sodium Topical Gel 1% or Reference Listed Drug (RLD) or Placebo gel to the arthritic target knee four times daily for 4 weeks.

The Western Ontario and McMaster Universities Osteoarthritis Index (WOMAC Likert version 3.1) pain score for the target knee and pain on movement (POM) on a Visual Analog Scale (VAS) for both the knees will be recorded on Week 2 and Week 4 from the start of the treatment.

Acetaminophen (paracetamol) tablets will be given to the subjects for use as a rescue medication or for the treatment of aches and pains unrelated to knee pain such as headache during treatment period (except 3 days prior to Visit 4 and Visit 5). Maximum allowed dose of acetaminophen (paracetamol) will be 2 g/day. Consumption of rescue medications in terms of number of tablets consumed will be monitored.

Subject diary will be provided to subjects to record study medication gel application, rescue medication, side effects, and concomitant medication details. Subject diary will be used to evaluate drug application compliance.

Physical examination will be conducted during each visit (except at the start of run-in period visit). Application site reaction assessment will be conducted on each visit after start of run-in period.

[figure not shown]
A standard 12-lead ECG will be recorded after 5 minutes of rest in the supine position on screening visit and on end of study visit. Vital signs will be measured after 5 minutes of rest (sitting) on each visit.

Serum pregnancy test for females of childbearing potential will be performed at screening and end of treatment visit. The urine pregnancy test can be performed if clinically indicated during other visits. If urine pregnancy is found to be positive, serum pregnancy will be drawn and analyzed for confirmation. If serum pregnancy test will found positive then patient will be excluded from the study and followed up.

Laboratory assessments like hematology and biochemistry will be performed during screening and end of study. The hematology and biochemistry at screening is to be performed within 14 days of baseline visit. If the gap between lab assessments and baseline visit will be more than 14 days, the lab assessments will be repeated at baseline visit. Laboratory investigations (if clinically significant) can be repeated once as per investigator's discretion.

Principal investigator or designee will contact the subjects approximately midway between the visit 3-4 and visit 4-5 for assessment of the well-being, adverse event, concomitant medication, and treatment compliance. Additional telephonic contact to reiterate the instructions regarding the use of rescue medications during 3 days prior to visits 4 and 5 will be done. Use of rescue medications by subjects during this period for intolerable pain will require rescheduling the visits in such a way that visits happen after at least 3 days of stopping rescue medication and subjects will be required to inform the center about the rescue medication use.

Study design is represented graphically in [Figure 1 Study Design](#).

**Figure 1 Study Design**

### 3.2 Sample Size

The study protocol, MYL-1601N-3002, is designed to demonstrate the Bioequivalence of Diclofenac Sodium Gel to Voltaren® Gel and the superiority of Diclofenac Sodium Gel and/or Voltaren® Gel over Placebo by using a clinical endpoint in patients with Osteoarthritis (OA) of the Knee. The clinical endpoint under consideration is the change from baseline Western Ontario and McMaster Universities Osteoarthritis Index (WOMAC) Likert (version 3.1) pain score. The framework under consideration and the sample size requirements were fine-tuned to satisfy the objectives of bioequivalence of test drug with the reference drug as well as superiority of the test drug to placebo. The sample size estimation is done to ensure 90% statistical power to test two hypotheses of bioequivalence and superiority, the hypotheses are briefly described below:

1. Null Hypothesis (Equivalence) is that the ratio of mean change from baseline in WOMAC Likert pain score between test and reference drug is less than or equal to 0.80 or greater than or equal to 1.25 Vs. the alternative hypothesis of ratio of mean change

from baseline in WOMAC Likert pain score between test and reference drug lies within the limits of 0.80 to 1.25, where the equivalence limit of 0.80 to 1.25 is adapted.

2. Null Hypothesis (Superiority): The mean change from baseline WOMAC Likert pain score of test or reference drug is greater than or equal to Placebo vs the alternative hypothesis of mean change from baseline WOMAC Likert pain score of test or reference drug is less than the placebo group.

To meet the requirement for the two hypotheses, three tests need to be performed to meet overall objectives:

- 1) Bioequivalence between Diclofenac Sodium Gel and Voltaren®
- 2) Superiority of Diclofenac Sodium Gel over Placebo
- 3) Superiority of Voltaren® over Placebo

Sample size calculations are performed under the following assumptions:

1. Mean ( $\pm$  Standard Deviation) reduction from baseline in WOMAC pain score is 5.85 ( $\pm 4.23$ ) for both active treatments.
2. Mean ( $\pm$  Standard Deviation) reduction from baseline in WOMAC pain score is 4.68 ( $\pm 4.89$ ) for placebo.

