### **3.2.1 Equivalence between test and reference product**

At least 261 subjects in Test Drug and 261 subjects in Reference Drug group will be required to show bioequivalence between Test and Reference product with 90% power and 5% level of significance assuming the following estimates:

- 1) 5% difference between Test and Reference of mean change in WOMAC score
- 2) 75 % inter subject coefficient of variation for Reference in WOMAC Score
- 3) Equivalence margin of 80.00-125.00%

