### **3.2.2 Superiority of test and reference product over placebo**

At least 363 subjects will be required in each arm to prove the superiority of test/reference drug to placebo with 90% power and 5% level of significance.

Considering 10% dropout rate, around 1212 subjects will be required to enroll in the study. All subjects will be randomized in 1:1:1 ratio.

Overall, to satisfy both hypotheses of equivalence and superiority, the highest sample size will be used in the study: 1212 subjects equally randomized to Test, Reference and Placebo treatments:

1. Diclofenac Sodium Gel: 404 subjects.

2. Voltaren® Gel : 404 subjects
3. Placebo: 404 subjects

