#### **5. HYPOTHESES TESTING**

##### **Hypothesis of Equivalence (Primary Endpoint)**

The null hypothesis to be tested is that the ratio of mean change from baseline in WOMAC Likert pain score between test and reference drug is less than or equal to 0.80 or greater than or equal to 1.25 vs the alternative hypothesis that this ratio is within the interval from 0.80 to 1.25:

$H_0: \mu_T / \mu_R \leq \theta_1$  or  $\mu_T / \mu_R \geq \theta_2$  versus  $H_A: \theta_1 < \mu_T / \mu_R < \theta_2$

Where  $\mu_T$  = mean of test treatment, and  $\mu_R$  = mean of reference treatment

Typically,  $H_0$  will be rejected with a type I error  $\alpha = 0.05$  (two 1-sided tests), if the 90% confidence interval for the ratio of means between test and reference products ( $\mu_T / \mu_R$ ) is contained within the interval  $[\theta_1, \theta_2]$ , where  $\theta_1 = 0.80$  and  $\theta_2 = 1.25$ .

A two-sided, 90% confidence interval on the test/reference ratio for mean change from baseline to Week 4 in total WOMAC Pain Subscale score for the Target Knee will be constructed using Fieller's method. The estimates of treatment means and standard errors will be obtained from Analysis of Covariance (ANCOVA) of the Test and Reference results, using a statistical model containing fixed effects for treatment and center and baseline WOMAC Pain Subscale score as covariate.

Bioequivalence will be established if the 90% confidence interval for the ratio of test/reference means is contained within the interval  $[0.80, 1.25]$  for Per Protocol population.

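### The power figures in SAP 3.2 do not follow from its own inputs or planned analysis, although the adopted size of 404 per arm can stand

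*SAP*

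**What the plan says.** SAP 3.2 gives the aim of the calculation: "The sample size estimation is done to ensure 90% statistical power to test two hypotheses of bioequivalence and superiority". It says the sample size was "fine-tuned to satisfy the objectives of bioequivalence of test drug with the reference drug as well as superiority of the test drug to placebo", and that "three tests need to be performed to meet overall objectives": equivalence, Test over placebo and Reference over placebo. Its general assumptions are that the mean "reduction from baseline in WOMAC pain score is 5.85" (SD 4.23) for both actives, against 4.68 (SD 4.89) for placebo.

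SAP 3.2.1 then sizes equivalence at 261 per arm for 90% power, using a "5% difference between Test and Reference of mean change in WOMAC score" and a "75 % inter subject coefficient of variation for Reference in WOMAC Score" with limits 0.80 to 1.25. SAP 3.2.2 says: "At least 363 subjects will be required in each arm to prove the superiority of test/reference drug to placebo with 90% power". A 10% dropout allowance takes 363 to 404 per arm, 1212 in total.

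For the analysis, SAP section 5 says the 90% interval for the ratio "will be constructed using Fieller's method". SAP 7.11.2.1 applies this to LS means of the unlogged change. SAP 7.11.2.2 tests each active against placebo by ANCOVA, with baseline score and center in the model. SAP 7.1.2 calls the study a success only if all three hypotheses are met.

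Protocol 12.6 repeats 261, 363, the CV and the undirected 5%. It gives no means or SDs for superiority, so the mismatch is visible only in the SAP.

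**The concern.** A sample-size section should let a reader recover each stated number from its inputs and know what power the planned tests have. Here that fails in three places.

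- **Superiority:** 363 does not come from the stated means and SDs.
- **Equivalence:** the 90% at 261 belongs to a log-scale method that the SAP does not plan to use. The CV of 75% also differs from the 72% implied by 4.23/5.85.
- **Test effect:** the general assumptions put the Test/Reference ratio at 1.00, while the equivalence step puts it 5% away in an unstated direction. The assumed gap to placebo is only 1.17 points, so 5% of 5.85 (0.29 points) is a quarter of it.

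All three tests must succeed. A single 90% figure therefore hides how much the result depends on which Test effect is meant.

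**Working it through.** **Inputs.** Actives 5.85 (SD 4.23), placebo 4.68 (SD 4.89), from SAP 3.2. CV 75%, 5% difference and limits 0.80 to 1.25, from SAP 3.2.1. Superiority is two-sided at 0.05 (Protocol 12.3.2); equivalence uses two one-sided tests at 0.05. Powers are t-based and unadjusted unless stated.

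**1. Reproducing 261.** On the log scale, sigma = sqrt(ln(1 + 0.75²)) = 0.668 and SE = 0.668 × sqrt(2/261) = 0.0585. At ratio 0.95 the standardised distances to the limits are ln(0.95/0.80)/0.0585 = 2.94 and ln(1.25/0.95)/0.0585 = 4.69, giving 90%. The smallest n for 90% is 261 at 0.95, 261 at 1/0.95 = 1.053, 254 at 1.05 and 195 at 1.00. So 261 reproduces, but equally for Test worse or Test better.

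**2. The same 261 under Fieller.** The interval lies inside the limits when both T − 0.80R and 1.25R − T are significantly positive. In units of the Reference mean, at ratio 0.95:
- lower: 0.15 / (0.75 × sqrt(1.64/261)) = 2.52
- upper: 0.30 / (0.75 × sqrt(2.5625/261)) = 4.04

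Power is 80%, and 85% at ratio 1.05. At ratio 0.95 it is 91% with 363 and 93% with 404. With SD 4.23 in place of CV 75%, 261 gives 83%.

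**3. The 363.** n = (1.960 + 1.282)² × (4.23² + 4.89²) / 1.17² = 320.9, or 322 t-based. At 363, SE = sqrt(41.805/363) = 0.339 and 1.17/0.339 = 3.45, giving 93%. At 404, SE = 0.322 and the power is 95%. A common SD of 4.89 gives 367.1, so 368 (369 t-based); a common SD of about 4.86 would be needed for 363. The enrolment step does reproduce: 363/0.9 = 403.3, so 404, and 3 × 404 = 1212.

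**4. Carrying an adverse 5% into superiority.** 0.95 × 5.85 − 4.68 = 0.8775. Then 0.8775/0.339 = 2.59 gives 73% at 363, and 0.8775/0.322 = 2.73 gives 78% at 404.

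**5. All tests on one set of inputs** (SDs 4.23/4.89; joint power by simulation of 2,000,000 trials with a shared placebo arm):

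| Per arm | Ratio | Test vs placebo | Reference vs placebo | Equivalence (Fieller) | All three |
|---|---|---|---|---|---|
| 363 | 0.95 | 73% | 93% | 92% | 69% |
| 363 | 1.00 | 93% | 93% | 99% | 88% |
| 363 | 1.05 | 99% | 93% | 95% | 89% |
| 404 | 0.95 | 78% | 95% | 95% | 74% |
| 404 | 1.00 | 95% | 95% | 99% | 91.5% |
| 404 | 1.05 | 99.5% | 95% | 97% | 93% |

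If 404 per arm enter mITT and 363 of them enter PP (an assumption), all three succeed in 73%, 91% and 91% at the three ratios.

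**6. Effect of ANCOVA.** If covariates explain a share v of the variance, SE² is multiplied by 1 − v. The documents give no v. For assumed v of 0/10/20/30/40%, Test vs placebo power at ratio 0.95 is 73/78/82/87/92% at 363 and 78/82/86/90/94% at 404. Reaching 90% needs v of about 37% at 363 or 29% at 404.

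**The case against.** The strongest reply is that the plan meets its claim on its own terms. SAP 3.2.1 and 3.2.2 attach 90% to each hypothesis separately, and with equal actives each test exceeds 90% at both 363 and 404. A 5% difference is also a reasonable cautious allowance for an equivalence calculation, with superiority sized at the expected mean. The excess of 363 over 322 and the CV of 75% against 72% both err on the safe side, and 261 was never the adopted size. The planned ANCOVA would add power that the unadjusted figures leave out.

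Most of this stands, and it is why the point is minor. What remains is that SAP 3.2 presents 5.85 as the assumption for both actives in all its calculations, then uses a different Test effect without saying why. It also states two sample sizes that do not match their inputs or planned method.

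A reader might infer more than the documents support:
- **That the 5% was meant as adverse, because 261 reproduces at 0.95.** It reproduces equally at 1/0.95, so the direction is unknown.
- **That the trial is underpowered.** This holds only for an adverse 5% without enough gain from covariates, and neither is established.
- **That 90% was promised for all three tests jointly.** The subsections do not say so.

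**Conclusion.** The stated power figures do not agree with their inputs or with the planned analysis.

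- 363 is not the 90% size for the stated SDs. The power there is about 93%, so the mismatch is conservative.
- The 90% at 261 is about 80% to 85% under the planned Fieller interval at CV 75%. The adopted size makes this good.
- The Test effect differs between the two steps. With equal actives there is no per-test shortfall, and all three tests succeed together with 88% (363) or 91.5% (404) probability. With an adverse 5%, Test vs placebo falls to 73% or 78% and all three to 69% or 74%.

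The adverse-case figures assume the SAP's means and SDs, normal data and no covariate gain. Nothing here biases an estimate, inflates the Type I error or alters any planned analysis. It gives no ground for cutting the size to 322 or for raising it. Severity: minor.

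**What to change.** Revise the text of SAP 3.2 only, and keep 404 per arm and 1212 in total.

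1. State the direction of the 5% Test-Reference difference.
2. Choose one SD or CV for the actives (4.23, that is CV 72%, or CV 75%) and use it for every test.
3. State the SDs and formula behind 363, or report about 93% power at 363 for SDs 4.23/4.89.
4. Replace the 90% attached to 261 with Fieller power on the chosen SD: at ratio 0.95, about 80% for CV 75% or 83% for SD 4.23.
5. Add one table of power per test and for all three jointly, at ratios 0.95, 1.00 and 1.05 and at 363 and 404 per arm, labelled as unadjusted with a note that ANCOVA may raise it. The table in the working serves if SD 4.23 is chosen; it must be rerun if CV 75% is chosen.

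Carry the wording into Protocol 12.6 only when the protocol is next amended, because Protocol 14.6 requires sponsor and IEC/IRB approval of revisions. The change needs no extra patients, procedures or analyses. Its one drawback is that the stated power looks less favourable in the adverse scenario.
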